2.2 Background

Chronic HF continues to be a major cause of mortality, hospitalisations, and suboptimal quality of life. Even with the best possible treatment, the 5-year survival rate for HF patients is worse than for most cancers (Braunwald 2015). Heart failure affects 2% of the Western population, increases to 10% over the age of 65 years, and up to 20% over the age of 75 years (Go et al 2014). The proportion of the Western population over the age of 65 years is expected to increase to over 30% by year 2050 and the costs of HF to society are expected to triple between years 2010 and 2030. Heart failure is currently broadly divided into three categories based on the systolic function of the left ventricle: (1) HFrEF (LVEF $< 40\%$), (2) HFmrEF (LVEF 40-49%), and (3) HFpEF (LVEF $\geq 50\%$). Together, HFmrEF and HFpEF account for 55% of HF cases; HFpEF and HFrEF are distinct clinical phenotypes with differing underlying pathophysiology, while HFmrEF appears to share some features of both HFrEF and HFpEF whilst remaining a possible independent category. Over recent years, there has been a drive to include HFmrEF patients into future HF studies in order to learn more about this category while evaluating new therapies for the treatment of either HFpEF or HFrEF. To further increase knowledge about this condition, patients with HFmrEF will be included in the current study.

Heart failure with preserved ejection fraction is overrepresented in elderly and in women. Mortality in the community approaches 25% at one year. In a comparison of trial populations, the prognosis in HFpEF is 50-75 deaths and 40-75 HF hospitalisations per 1000 patient-years, whereas in stable coronary disease it is 10-30 deaths and 5-10 hospitalisations per 1000 patient-years and has improved further with modern therapy. Thus, novel interventions for coronary artery disease have little potential, whereas for HFpEF, novel treatment is both a critical unmet need and of great public health impact, if successful (Butler et al 2014, McMurray et al 2012).

A novel paradigm for HFpEF pathophysiology states that co-morbidities (renal disease, hypertension, obesity, and diabetes) lead to a global inflammatory state, leading to immune cell recruitment and endothelial and coronary microvascular dysfunction, with distinct

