9.2 Sample Size Determination

	Part A	Part B
Enrolled	Estimated 1100 participants	Estimated 1350 participants
Randomised	Estimated 660 participants	Estimated 820 participants
Participants with complete safety data	Estimated 600 participants	Estimated 745 participants

Part A

The sample size selection was based on the following assumptions:

- Change from baseline in 6MWD is approximately normally distributed with a standard deviation of 70 meters (Nassif et al 2019).
- Change from baseline in KCCQ-TSS is approximately normally distributed with a standard deviation of 18 points.

Approximately 660 participants randomised, of which we estimate approximately 600 will have complete safety data, and 1:1:1 allocation, is chosen to have enough participants exposed to AZD4831 at the therapeutic dose to fulfil the minimum requirement in the ICH E1 guideline on population exposure, taken together with Part B of this study, as well as a second function and symptom study with a similar design as Part B, and Phase 1 studies completed ahead of submission.

With 85% power at a significance level of $\alpha = 0.05$, 200 participants per arm will allow detection of a difference of 6.0 points in mean change from baseline between active and placebo in KCCQ-TSS comparing each active arm with placebo. The critical value for statistical significance is 3.9 points. The corresponding numbers for 6MWD are 21 meters and 14 meters. Calculations of detectable differences and critical values are based on ANCOVA, which will also be used for the analysis.

The potential effect of informative censoring, including all-cause mortality, will be considered during the analysis of the data and interpretation of the results, but not taken into account in the sample size calculations for Part A.

Part B

For part B, we assume that the type 1 error is controlled using Bonferroni adjustment (this is not necessarily the choice of method for type 1 error control in the analysis phase).

For KCCQ-TSS, we assume that:

- Change from baseline in KCCQ-TSS is approximately normally distributed with an expected value dependent on the baseline score, treatment group and treatment-by-baseline interaction, and with a residual error of 18.

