9.4.2 Efficacy

9.4.2.1 Primary Endpoint(s)

The primary efficacy endpoints are KCCQ-TSS and 6MWD and the primary efficacy variables are change from baseline in KCCQ-TSS and 6MWD at 16 weeks for Part A and at 24 weeks for Part B.

All primary variables will be analysed using ANCOVA with baseline and treatment group as covariate, and will be adjusted for the stratification factor for neutrophil count (Part A and Part B), comparing the AZD4831 doses versus placebo. For Part A, both single doses alone, and both doses pooled, will be compared with placebo. In Part B, a term for treatment by-baseline interaction will be included as independent variable in the model for KCCQ-TSS.

Model summary in Part A:

- 6MWD change from baseline at 16 Weeks:

$$\begin{aligned} E[CHG_{6MWD} | BASE_{6MWD}, TRT] \\ = \beta_0 + \beta_1 * BASE_{6MWD} + \beta_2 * STRATA + \beta_3 * TRT \end{aligned}$$

- KCCQ-TSS change from baseline at 16 Weeks:

$$\begin{aligned} E[CHG_{KCCQ-TSS} | BASE_{KCCQ-TSS}, TRT] \\ = \beta_0 + \beta_1 * BASE_{KCCQ-TSS} + \beta_2 * STRATA + \beta_3 * TRT \end{aligned}$$

Model summary in Part B

- 6MWD change from baseline at 24 Weeks:

$$\begin{aligned} E[CHG_{6MWD} | BASE_{6MWD}, TRT] \\ = \beta_0 + \beta_1 * BASE_{6MWD} + \beta_2 * STRATA + \beta_3 * TRT \end{aligned}$$

- KCCQ-TSS change from baseline at 24 Weeks:

$$\begin{aligned} E[CHG_{KCCQ-TSS} | BASE_{KCCQ-TSS}, TRT] \\ = \beta_0 + \beta_1 * BASE_{KCCQ-TSS} + \beta_2 * STRATA + \beta_3 * TRT + \beta_4 \\ * BASE_{KCCQ-TSS} * TRT \end{aligned}$$

Where TRT indicates randomized treatment group; STRATA indicates neutrophil baseline strata; BASE_{6MWD} and CHG_{6MWD} indicates baseline and change from baseline in 6MWD, respectively; and BASE_{KCCQ-TSS} and CHG_{KCCQ-TSS} indicates baseline and change from baseline in KCCQ-TSS, respectively.

Subgroup analyses will be performed for both primary endpoints.

Primary Efficacy Objectives Related Estimands:

Part A:

Treatment: Treatment with 2.5 mg or 5 mg AZD4831 compared to placebo, administered in addition to optimal back-ground therapy for co-morbidities.

Population: Patients that fulfill all of the inclusion criteria, none of the exclusion criteria and have available measurements of the efficacy endpoint at baseline and 16 weeks.

Endpoint: Change from baseline to 16 weeks in KCCQ-TSS and 6MWD.

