Intercurrent events: Patients with intercurrent events resulting in missing assessments of the primary endpoints, eg, terminal events or withdrawal from the study, is expected to be very few and will be excluded from the analysis (principal stratum strategy). Other intercurrent

events, eg, premature discontinuation of study treatment, will be ignored (treatment policy strategy).

Population-level summary: Difference in adjusted mean change from baseline between groups.

Missing data will not be imputed.

Part B:

Treatment: Treatment with either 2.5 mg or 5 mg AZD4831 compared to placebo, administered in addition to optimal back-ground therapy for co-morbidities.

Population: Patients that fulfill all of the inclusion and none of the exclusion criteria.

Endpoint: Change from baseline to 24 weeks in KCCQ-TSS and 6MWD.

Intercurrent events:

- Deaths will be handled by a While-alive strategy, implemented by using the change from baseline to 24 weeks or last measurement prior to death (if earlier than 24 weeks).
- Intercurrent events other than deaths will be handled by a Treatment-policy strategy, ie, measurements will be collected and used in the statistical analysis regardless of the occurrence of the event

Population-level summary: Between group difference in mean change from baseline at 24 weeks or prior to death, if earlier. For KCCQ-TSS, this will be a function of baseline values.

For patients with missing measurements for reasons other than death, a multiple imputation scheme will be employed, which differentiates between monotonous and non-monotonous missing data. Monotonous missing data are where observations are consistently missing after a point in time whereas non-monotonous missing data are missing observations followed by at least one recorded observation. For monotonous missing data, retrieved dropouts (patients remaining in the study despite same intercurrent events as drop-outs) will be used to impute missing values or, if there are too few retrieved dropouts, a Jump-to-reference approach utilizing placebo patients will be applied.

As a supplementary approach, analyses where deaths are combined with the outcome variables in a Composite strategy will be conducted, and will be described in the SAP for Part B.

Methods for multiplicity control, both Part A and Part B:

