4.2 Endpoint Analyses

This section covers details related to the endpoint analyses such as primary, secondary, and exploratory endpoints including sensitivity and supportive analyses.

Primary estimand

The primary estimand is defined by the following attributes:

- **Endpoint:** Change from baseline in variable at analysis timepoint.
- **Treatment:** Randomised treatment group (regardless of actual received treatment), AZD4831 2.5mg/5mg or placebo, administered in addition to optimal background therapy for co-morbidities.
- **Population:** Subjects aged ≥ 40 years with an established diagnosis of HF with LVEF $> 40\%$, and at least one or more of structural heart disease, signs of increased left ventricular filling pressure, signs of significant diastolic dysfunction, or a recent hospitalisation for decompensated HF and alive. This is implemented on evaluable subjects defined by a subset of FAS (see Table 2) which have available measurements of the efficacy endpoints at baseline and analysis timepoint.
- **Population-level summary:** Difference in adjusted mean change from baseline to analysis timepoint or adjusted geometric mean ratio.
- **Handling of intercurrent events:** Treatment policy strategy combined with principal stratum strategy
 - Initiation or change of concomitant medication and permanent premature discontinuations of IP will be handled by a treatment policy strategy, i.e., ignoring these intercurrent events, implemented by including all available data.
 - Subjects with intercurrent events resulting in missing assessments of the primary endpoints, e.g., terminal events or withdrawal from the study, are expected to be very few and will be excluded from the analysis (principal stratum strategy).

Supplementary estimands

Supplementary analyses of the primary objectives will be conducted using four different supplementary estimands. The treatment attribute for the supplementary estimands is the same as for the primary estimand.

For the first supplementary estimand, the other attributes are the following:

- **Endpoint:** Change from baseline in variable at analysis timepoint.
- **Population:** Subjects aged ≥ 40 years with an established diagnosis of HF with LVEF $> 40\%$, and at least one or more of structural heart disease, signs of increased left ventricular filling pressure, signs of significant diastolic dysfunction, or a recent hospitalisation for decompensated HF. Implemented by FAS.

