 - Deaths will be handled by a while-alive strategy, implemented by including the last available efficacy assessment in the analysis.
 - Subjects with intercurrent events resulting in missing assessments of the primary endpoints other than death are expected to be very few and will be excluded from the analysis (principal stratum strategy).

Table 2 Overview of efficacy objectives, endpoints and estimands

Statistical category	Endpoint	Population	Handling of intercurrent events	Population level summary (analysis)	Details in section
Objective 1: To evaluate the effect of AZD4831 on KCCQ-TSS					
Primary analysis of primary endpoint targeting	KCCQ-TSS change from baseline at 16 weeks	Principal stratum of FAS	Treatment policy strategy combined with principal stratum strategy	Difference in adjusted mean change from baseline at 16 weeks (ANCOVA)	4.2.1.4

Statistical category	Endpoint	Population	Handling of intercurrent events	Population level summary (analysis)	Details in section
primary estimand					
Sensitivity analysis of primary endpoint targeting the primary estimand	KCCQ-TSS change from baseline at 16 weeks	Principal stratum of FAS	Treatment policy strategy combined with principal stratum strategy	Difference in adjusted mean change from baseline at 16 weeks (ANCOVA)	4.2.1.5
Supplementary analysis of primary endpoint targeting first supplementary estimand	KCCQ-TSS change from baseline at 16 weeks	FAS	Treatment policy strategy combined with hypothetical strategy	Difference in adjusted mean change from baseline at 16 weeks (MMRM)	4.2.1.6
Supplementary analysis of primary endpoint targeting second supplementary estimand	Composite of KCCQ-TSS change from baseline at 16 weeks and death	FAS	Treatment policy strategy combined with composite strategy	Difference in adjusted median change from baseline at 16 weeks (Rank ANCOVA and Hodges-Lehmann)	4.2.1.6
Supplementary analysis of primary endpoint targeting third supplementary estimand	KCCQ-TSS change from baseline at 16 weeks	Principal stratum of FAS	Treatment policy strategy combined with principal stratum strategy	Difference in adjusted mean change from baseline at 16 weeks (ANCOVA)	4.2.1.6

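### Part A's primary estimand is a complete-case analysis labelled a principal stratum, non-death withdrawals stay only in the MMRM, and supplementary estimand 4 contradicts itself

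*SAP*

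**What the plan says.** **Primary estimand.** SAP 4.2 describes the population as patients with HF who meet one of several criteria, ending with "a recent hospitalisation for decompensated HF and alive". It implements this on "evaluable subjects defined by a subset of FAS (see Table 2) which have available measurements of the efficacy endpoints at baseline and analysis timepoint". Subjects whose intercurrent event leaves the endpoint missing are dropped: "terminal events or withdrawal from the study, are expected to be very few and will be excluded from the analysis (principal stratum strategy". Protocol 9.4.2.1 agrees for Part A. Its population must "have available measurements of the efficacy endpoint at baseline and 16 weeks", and it adds: "Missing data will not be imputed". Stopping study drug is handled by treatment policy, and Protocol 7.1 asks such participants to stay in the study, so their data are kept.

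**Back-up analyses.** Protocol 9.2 says of Part A: "The potential effect of informative censoring, including all-cause mortality, will be considered during the analysis of the data and interpretation of the results". In SAP Table 2 the row "Sensitivity analysis of primary endpoint targeting the primary estimand" has the same population as the primary analysis. The four supplementary estimands in SAP 4.2 are:

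- **1:** FAS, MMRM, with death treated as a non-informative event.
- **2:** a composite with death as the worst outcome. It is described as implemented by FAS, with only treatment-policy and composite strategies in its heading. Its last bullet then excludes non-death missing subjects as a principal stratum.
- **3:** the primary rule, also dropping those who stopped study drug.
- **4:** while-alive for death, using the last available assessment, with non-death missing subjects excluded. Its population sentence repeats the primary one: "evaluable subjects defined by a subset of FAS (see Table 2) which have available measurements of the efficacy endpoints at baseline and analysis timepoint".

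Under Objective 2 (6MWD), Table 2's composite row names KCCQ-TSS.

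**Part B.** Protocol 9.4.2.1 uses while-alive for death. Other missing values are multiply imputed; for monotone missingness this is from retrieved dropouts, or by jump-to-reference if these are too few.

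**The concern.** A principal stratum is defined by what a patient's status would be under both treatments. The Part A set is selected on being alive and observed under the arm actually assigned. The two coincide only if treatment does not affect who is missing. The definition does not say that; the expectation of very few exclusions concerns how many are missing, not which ones.

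If missingness is related to response and also unequal between arms, the treatment contrast is biased, in a direction that depends on the split. The back-up matters for that reason, and for non-death withdrawals it comes down to one analysis. The same estimand also serves the Week 48 secondary endpoints, where few exclusions is harder to assume. Separately, estimand 4 cannot be programmed as worded.

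**Working it through.** **Step 1. Reproduce the plan's figure.** Inputs: 200 per arm, 6.0 points and 21 m (Protocol 9.2), SD 20 for KCCQ-TSS (SAP 2, correcting the protocol's 18), SD 70 m for 6MWD.

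- KCCQ-TSS: SE = 20 x sqrt(2/200) = 2.00; 6/2.00 - 1.96 = 1.04, power 85.1%; critical value 1.96 x 2.00 = 3.92. The plan says 85% and 3.9.
- 6MWD: SE = 70 x sqrt(2/200) = 7.0; power 85.1%; critical value 13.7 m. The plan says 14 m.

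**Step 2. Estimand 4, rule against rule.** The population needs a value at the analysis timepoint. The death rule includes the last assessment of subjects who died. Someone who dies before having a Week 16 value fails the first rule, so the second never applies to them. Applied literally, the deaths drop out again and the while-alive strategy has no effect.

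**Step 3. Who keeps non-death withdrawals.** The primary, the sensitivity population and estimands 2, 3 and 4 exclude them. Only estimand 1 does not, and a leaver informs an MMRM only through a post-baseline value. KCCQ-TSS has Week 12 (SAP 4.2.3.4). For 6MWD, protocol Figure 1 lists no test between baseline and Week 16 except at the early discontinuation visit (EDV); the 6MWT row of protocol Table 1 is missing from the text.

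**Step 4. Size of the bias under no true effect.** Formal test: pooled AZD4831 (440) versus placebo (220), first Holm step 0.025, z = 2.241 (SAP 3.3.4). If leavers are g points worse than stayers in both arms and fractions mA and mP are missing:

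bias = g x (mA - mP); SE = 20 x sqrt(1/nA + 1/nP), with nA and nP the observed numbers.

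The splits and g = 10 to 20 points are assumptions.

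| Missing, active vs placebo | mA - mP | Bias (points) | SE | Critical difference | Rejection |
|---|---|---|---|---|---|
| equal | 0 | 0 | - | - | 0.025 |
| 9/440 vs 2/220 (2.0% vs 0.9%) | 0.0114 | 0.11 to 0.23 | 1.662 | 3.73 | 0.025 to 0.026 |
| 25/440 vs 5/220 (5.7% vs 2.3%) | 0.0341 | 0.34 to 0.68 | 1.681 | 3.77 | 0.028 to 0.037 |
| 50/440 vs 10/220 (11.4% vs 4.5%) | 0.0682 | 0.68 to 1.36 | 1.712 | 3.84 | 0.037 to 0.075 |
| 31/440 vs 29/220 (7.0% vs 13.2%) | -0.0614 | -0.61 to -1.23 | 1.753 | 3.93 | bias against the drug |

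For 6MWD with leavers 35 to 70 m worse, the three active-higher splits give 0.4 to 0.8, 1.2 to 2.4 and 2.4 to 4.8 m, against critical differences of 13.0 to 13.4 m.

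**Step 5. The one rate in the documents.** Protocol 2.2: "the prognosis in HFpEF is 50-75 deaths and 40-75 HF hospitalisations per 1000 patient-years". With 1 - exp(-rate x weeks x 7/365.25), deaths are 1.5% to 2.3% by Week 16 (10 to 15 of 660) and 4.5% to 6.7% by Week 48 (30 to 44 of 660). This covers deaths only; no withdrawal rate is given.

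**Step 6. What added imputation would do.** Simulated at 11.4% vs 4.5% with gaps of 10/20 points, placebo-based imputation of the full FAS cuts the bias from 0.68/1.41 to 0.34/0.72 if 80% of leavers have EDV values, but only from 0.66/1.36 to 0.59/1.20 if none do. It reduces the bias without removing it, which is why a tipping-point analysis should go with it.

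**The case against.** The strongest objection is that the decisive text cannot be seen. SAP 4.2.1.3 to 4.2.1.6 (missing data, primary, sensitivity and supplementary analyses) is in the contents list but not readable here. The SAP amendment history for version 2 records a newly defined sensitivity analysis and a distinction between intercurrent events and missing data. A reader might infer that the SAP has no missing-data assumption or no sensitivity method. The documents do not support that; only the definitions can be judged. Nor does the sensitivity row's shared population show a gap, because a sensitivity analysis of an estimand should keep its population.

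A reader might also infer that drug-related rash removes patients from the primary analysis. It does not: rash forces study drug to stop, but those patients stay in follow-up and their data are used. Withdrawal is expected to be uncommon (Protocol 7.2). Any assessment on days 100 to 141, including an EDV, can serve as Week 16 (SAP 3.3.2). KCCQ is also completed at home in Week 15, although the readable visit windows cover on-site assessments only.

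Finally, the larger biases need a 2.5:1 split and, at the top, a gap of one full SD. The 60/660 = 9.1% total is the plan's allowance for incomplete safety data, so it cannot be read as a Week 16 missingness rate or as evidence of an inflated error rate.

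All of this stands and limits the size. It does not remove the conflict inside estimand 4, nor the fact that the definitions keep non-death withdrawals in only one analysis. Estimand 4's summary measure does make its intent clear, and SAP 4.2.2.1 says 6MWD uses the same estimands as KCCQ-TSS, so the Table 2 entry is a copying slip.

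**Conclusion.** The point holds for the estimand definitions in SAP 4.2, Table 2 and Protocol 9.4.2.1. The primary analysis is complete-case under a label that does not fit, with no stated assumption in the definition about who is missing. Deaths return in supplementary estimands 1 and 2 and, by intent, 4. Non-death withdrawals return only in the MMRM, which by Figure 1 has little interim 6MWD data. Estimand 4 is wrong as written, whatever the missingness rate.

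The numerical effect rests on assumed missing splits and leaver gaps. It is negligible if missingness is rare or balanced, and material only with substantial, unequal, response-related missingness. Severity is minor to moderate: Part A is not pivotal, unless Part B does not start or progress, in which case it becomes the final analysis for the CSR (SAP 3.1). Confidence is medium because of the unreadable sections.

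**What to change.** (a) Define estimand 4's population as FAS subjects with a baseline value and either a value at the analysis timepoint or, if they died before it, a last post-baseline assessment before death.

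(b) Unless SAP 4.2.1.5 or 4.2.1.6 already provides it, add a supplementary all-FAS treatment-policy analysis of both primaries using Part B's handling: while-alive for death, and imputation from retrieved dropouts, or jump-to-reference if too few, for other missing data. Add a tipping-point analysis. Leave the primary analysis unchanged, and have staff blinded to Part A specify the addition.

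(c) As minor wording, call the primary complete-case, align estimand 2's strategy heading with its exclusion, and put 6MWD in Table 2's Objective 2 composite row.

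The cost is text edits and programming, with no new data. The primary analysis keeps its power. The added analysis has less: with 9.1% missing, a 6-point effect, SD 20 and leavers imputed with no drug effect, simulation with Rubin's rules gives about 80% for one dose versus placebo at 0.05 (complete-case 85.1%) and 84% for pooled versus placebo at 0.025 (complete-case 88.9%). A closed form that treats imputed values as observed gives 81.6% and 85.6%, which is slightly optimistic.
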